1.2.4 Induction Dose of Pembrolizumab on Day -21

A major gap in knowledge in the field is the optimal timing of checkpoint inhibition in relation to RT and/or chemotherapy other therapies in the induction of an abscopal effect. The available data suggests that the timing of the first dose of checkpoint inhibition in relation to other therapies may be critical ([Dewan et al., 2009](#)), including data from randomized controlled trials comparing the initiation of checkpoint inhibition concurrently vs non-concurrently with chemotherapy([Lynch et al., 2012](#); [Reck et al., 2013](#)). Dewan et al. found that delaying the initiation of anti-CTLA-4 antibody until a few days after the completion of RT reduced the therapeutic effect on the primary and secondary (non-irradiated) tumor, as compared to initiating

antibody treatment on the first or final day of RT (RT was given in 3 fractions of 6 Gy each) ([Dewan et al., 2009](#)). To date, no study has directly compared the initiation of checkpoint blockade on the same day as RT initiation *vs* prior to RT initiation.

Some data support the initiation of checkpoint blockade on the same day as RT. Deng et al demonstrated an abscopal effect from the combination of PD-L1 blockade and RT, and PD-L1 blockade (administered every 3 days for a total of 4 times) was initiated on the day of IR or 1 day before IR ([Deng et al., 2014](#)). However, the initiation of PD-1 axis blockade on the same day as (*vs* prior to) RT/chemotherapy can theoretically have a detrimental effect: cytotoxic T cells which become newly primed and recruited via anti-PD-1 therapy may be destroyed by RT and/or chemotherapy. Deng et al did not directly compare different administration schedules of PD-1/L1 with regard to RT.

Other data or concepts support the initiation of checkpoint blockade prior to RT:

- Collaborators in the current trial demonstrated an abscopal effect from the combination of PD-1 blockade and RT, and pharmacologic PD-1 blockade was initiated one day prior to RT ([Park et al., 2015](#)). While Park et al did not directly compare different administration schedules of PD-1 Ab with regard to RT, the investigators found a similar abscopal effect in PD-1 knockout models, suggesting that baseline inhibition of PD-1 can induce an abscopal response.
- Administration of carboplatin/paclitaxel in patients requires pre-medication with corticosteroids to reduce the likelihood and severity nausea/vomiting and hypersensitivity reactions. However, the well-known immunosuppressive effect of corticosteroids, despite their short half-life, may blunt the effect of immune checkpoint inhibition. The administration of pembrolizumab prior to the administration of cytotoxic agents may avoid this issue.

1.3 CUP Patient Population

In addition to the poor prognosis of CUP patients despite treatment, CUP was selected because these tumors exhibit molecular characteristics that may increase their susceptibility to PD-1 blockade. Recent examination of 70 CUP cases revealed PDL1-expressing cancer cells in 21% of tumors ([Gatalica et al., 2014](#)), a frequency comparable to that found in other tumor types where single-agent PD-1 therapy has shown activity. A high mutation load was detected in 13% of tumors of unknown primary; this frequency was the 16th highest out of >50 tumor types profiled using targeted next generation sequencing of >300 cancer genes (personal communication, unpublished data). A high mutation load has been shown to correlate with pembrolizumab activity in NSCLC ([Rizvi et al., 2015](#)).

At most cancer centers with a high volume of CUP patients, including at the Mayo Clinic, patients generally start standard chemotherapy with their local community oncologist prior to being seen at the larger center. This referral pattern is primarily for logistic reasons – i.e., inability to secure an immediate appointment after the completion of the diagnostic workup, which itself can be time-consuming.

Accordingly, the vast majority of CUP patients seen at large centers have already initiated first-line therapy. While there is no standard front-line regimen, platinum-, taxane-, and/or gemcitabine combination regimens are common, and one regimen has not been shown to be superior compared to another.

The rationale in the current study is to take advantage of this referral pattern by allowing the enrollment of patients who have started front-line therapy.

1.4 Potential Safety Concerns

1.4.1 Pembrolizumab

For pembrolizumab monotherapy, in clinical trials completed to date, most immune related adverse events associated with pembrolizumab were mild (grade 1–2), some were severe, and a few were lethal. Refer to the Investigator's Brochure (IB) for detailed safety information on MK-3475. In brief, the most recent IB (updated 2/17/2017) presents safety data available from the Sponsor's Reference Safety Dataset (n=2799), a locked and verified dataset with pooled data from clinical trials in melanoma and NSCLC, as part of the Sponsor's product development of pembrolizumab. The Reference Safety Dataset comprises safety data from locked KN001, KN002, KN006, and KN010 [Sec. 1]. The Reference Safety Dataset is the dataset from which frequencies in this IB are derived. The 5 most frequently reported AEs were: fatigue (37.3%), nausea (24.5%), decreased appetite (22.5%), diarrhea (22.3%), and cough (22%). The 5 most frequently reported serious AEs (SAE) were pneumonia (3.0%), pleural effusion (1.7%), pneumonitis (1.6%), dyspnea (1.6%) and pulmonary embolism (1.5%). The 5 most frequently reported AEs considered drug-related by the investigator were fatigue (24.2%), pruritus (16.7%), rash (13.8%), diarrhea (12.3%), and nausea (10.9%). The 5 most frequently reported SAEs considered drug-related by the investigator were pneumonitis (1.6%), colitis (0.9%), diarrhea (0.6%), pyrexia (0.4%), and autoimmune hepatitis (0.3%).

1.4.2 Combination of Pembrolizumab and RT

In the current trial, because RT may be given to lung or liver metastases, potential lung and liver toxicities of pembrolizumab are described further here:

- Pneumonitis in association with pembrolizumab (according to IB 22-May-2015):
 - Frequency/grade: Pneumonitis was quantitatively assessed using the following adverse events of special interest (AEOSI) preferred terms: acute interstitial pneumonitis, interstitial lung disease, pneumonitis, and idiopathic pneumonia syndrome. Out of a total of 1562 subjects with melanoma or lung cancer (P001 and P002) treated with pembrolizumab (2 mg/kg q3w, 10 mg/k2 q3 w, or 10 mg/k2 q2w), AEOSI of pneumonitis were identified in 45 subjects (2.9%), of which 42 (2.7%) were considered drug related. Serious AEOSI were identified in 1.2% of subjects, and all serious AEOSI were considered by the Investigators to be drug related. One subject died due to pneumonitis (interstitial lung disease, dose level 10 mg/k2 q3w). By worst toxicity grade, 14 subjects (0.9%) experienced Grade 1 pneumonitis, 15 subjects (1.0%) experienced Grade 2 pneumonitis, 11 subjects (0.7%) experienced Grade 3 pneumonitis, and 2 subjects (0.1%) experienced Grade 4 pneumonitis. For "interstitial lung disease," 1 subject (0.1%) experienced Grade 1 interstitial lung disease, 1 subject (0.1%)

experienced Grade 3 interstitial lung disease, and 1 subject (0.1%) experienced Grade 5 interstitial lung disease.

- Time to development of pneumonitis: Data are available from the 38 patients with previously-treated NSCLC treated with MK-3475 10mg/kg every 3 weeks in P001, of whom 2 patients have been reported with pneumonitis and one patient has been reported with steroid-responsive pulmonary edema. Two cases were grade 2; the case of pulmonary edema was grade 3. These cases began as early as four days after the first dose to several cycles (Week 18) after the first dose.
- Hepatic abnormalities in association with pembrolizumab (according to IB 22-May-2015): Hepatic AEOSI was quantitatively assessed using the following AEOSI preferred terms: hepatitis, autoimmune hepatitis, hepatitis acute, hepatitis fulminant and drug-induced liver injury. Out of a total of 1562 subjects, hepatic AEOSI were identified in 8 subjects (0.5%). All the hepatic AEOSI were considered drug-related. Serious hepatic AEOSI were identified in 2 subjects (0.1%); both were considered by the Investigators to be drug related. By worst toxicity grade, hepatitis was reported for 2 subjects (0.1%). The 2 instances were Grade 1 and Grade 3. Autoimmune hepatitis was reported for 6 subjects (0.4%). Two subjects (0.1%) experienced Grade 2 autoimmune hepatitis, 3 subjects (0.2%) experienced Grade 3 autoimmune hepatitis, and 1 subject (0.1%) experienced Grade 4 autoimmune hepatitis.

Delivery of RT to lung or liver lesion(s) in the current trial may theoretically cause an exacerbation of organ-specific toxicities and thus are considered in more detail as follows.

Radiation pneumonitis has been reported in patients who have undergone mediastinal radiation therapy for lung cancer, Hodgkin's lymphoma (HL), breast cancer, and other cancers that require radiation therapy to the thorax ([Carver et al., 2007](#)). A retrospective analysis of 1,911 patients who underwent combined-modality therapy for lung cancer demonstrated that the overall risk of radiation pneumonitis was 7.8% ([Roach et al., 1995](#)). Clinical factors that may increase the risk of radiation pneumonitis include concomitant chemotherapy, previous irradiation, and recent withdrawal of steroids ([McDonald et al., 1995](#)). Patient factors, such as lung function, age, and sex, do not adequately select patients at high risk for radiation pneumonitis or fibrosis ([Dehing-Oberije et al., 2009](#)). Radiation pneumonitis is typically a delayed acute reaction, usually occurring 1 to 3 months after completing mediastinal radiation therapy ([McDonald et al., 1995](#)). Patients who experience acute radiation pneumonitis will often have a self-limited course, with complete resolution of this process. However, a minority of patients may develop progressive pulmonary fibrosis, usually 6 to 24 months after treatment. Late complications of pulmonary fibrosis include cor pulmonale and respiratory failure ([Carver et al., 2007](#)). Both the V20 (ie, the percentage volume of both lungs minus the planning target volume [PTV] receiving 20 Gy) and the mean lung dose (MLD) correlate with the risk for radiation pneumonitis ([De Ruysscher et al., 2010](#)). In a landmark study ([Graham et al., 1999](#)), V20 was the single independent predictor of pneumonitis in a multivariate analysis. In this study, 42% of the patients received concurrent chemotherapy, and the incidence of grade ≥ 2 pneumonitis was 7% when the V20 was 22 – 31%. With the radiation doses we are proposing in this study, we expect V20 to be < 20% and therefore, the risk of radiation-related pneumonitis will be minimal. However, as a precaution to

reduce risk for thoracic toxicities following RT plus pembrolizumab, the following measures will be implemented:

- Strict limits on normal tissue doses and other aspects of radiation delivery will be mandated per the most updated standard of care and as recommended ([Tang et al., 2014](#)).
- Patients with recent serious pulmonary illness will be excluded (see section 3).
- Monitoring will include late lung toxicities, given that pneumonitis often does not appear until several months after radiation treatment is completed.

Radiation-Induced Liver Disease (RILD) usually develops 1-2 months after RT and describes a clinical syndrome composed of fatigue, ascites, elevated LFTs and abdominal pain. Emami et al ([Emami et al., 1991](#)) estimated the acceptable liver tolerance dose (TD5/5; tolerance dose that may cause 5% complication rate within 5 years) of 3000, 3500, and 5000 cGy when whole, 2/3, and 1/3 of the liver was radiated, respectively. This task force estimation is limited by the 2D treatment technique employed at the time. The Quantitative Analysis of Normal Tissue Effects in the Clinic (QUANTEC) ([Marks et al., 2010](#)) provides the more recent guidelines using the 3D dose/volume/outcome data. In this analysis, preexisting liver dysfunction (Child-Pugh B or C), mean liver dose and V30 (volume receiving 30 Gy or higher) were associated with RILD ([Pan et al., 2010](#)). Accordingly, patients with primary liver tumors have a lower radiation dose/volume threshold for developing RILD than patients with liver metastases. RILD data for partial liver radiation has been studied using the Lyman-Kutcher-Burman model by the investigators at the University of Michigan ([Dawson et al., 2002](#)). In this study, the rate of RILD grade 3 or higher within 4 months in 203 patients treated with 3D conformal radiation and concurrent hepatic arterial chemotherapy were analyzed. Although some patients received 90 Gy, no RILD was noted when the mean liver dose was <31 Gy. Therefore, in the current study, we will use the following liver constraints as described in QUANTEC to minimize liver toxicity: mean liver <= 30 Gy and >=700 ml of normal liver to receive <=15 Gy (which is a stricter constraint used for 5 fraction SBRT regimen).

The safety and tolerability of lung/liver RT in combination of pembrolizumab has not been extensively examined and, with the implementation of appropriate safeguards (see below: Eligibility, Study Design), is a focus of the current trial. The combination of pembrolizumab + concurrent radio(chemo)therapy is being examined in multiple trials in other tumor types:

- **Pembrolizumab, Combination Chemotherapy, and Radiation Therapy Before Surgery in Treating Adult Patients with Locally Advanced Gastroesophageal Junction or Gastric Cardia Cancer That Can Be Removed by Surgery NCT02730546 – This study is led by the PI of the current study ([name])**
 - Tumor: locally advanced gastroesophageal junction (GEJ) adenocarcinoma
 - Treatment: carboplatin/paclitaxel weekly for 5 weeks plus pembrolizumab every 3 weeks, plus concurrent RT
 - Location/schedule of RT: RT to GEJ at 41 Gy over 23 fractions
 - Estimated enrollment, N = 30
 - Dates study start, primary completion: Aug 2016, April 2018
 - Primary Outcome: Response

- Phase I Trial of MK-3475 and Concurrent Chemo/Radiation for the Elimination of Small Cell Lung Cancer (NCT02402920; for brevity, only “Part B” for extensive stage is shown):
 - Tumor: extensive SCLC (ECOG PS 0-2)
 - Treatment: Cis(carbo)platin/etoposide Days 1-3 (every 3 weeks) for up to 4 cycles, plus pembrolizumab on Day 1, plus concurrent RT
 - Location/schedule of RT: RT to chest at 45 Gy once a day for 15 days.
 - Estimated enrollment, N = 80
 - Dates study start, primary completion: July 2015, July 2023
 - Primary Outcome: MTD of MK 3475.
- A Randomized Multicenter Phase Ib/II Study to Assess the Safety and the Immunological Effect of Chemoradiation Therapy (CRT) in Combination with Pembrolizumab (MK-3475) Compared to CRT Alone in Patients with Resectable or Borderline Resectable Pancreatic Cancer (UVA-PC-PD101; NCT02305186):
 - Tumor: Resectable or borderline resectable pancreatic cancer (ECOG PS 0-1)
 - Treatment:
 - Experimental arm: Neoadjuvant capecitabine (825 mg/m² orally twice daily, M-F on days of RT) and RT plus pembrolizumab 200 mg IV every 3 weeks on days 1, 22, and 43 during concurrent chemoradiation.
 - Control arm: Chemoradiation alone.
 - Location/schedule of RT: RT to pancreas at 50.4 Gy in 28 daily fractions
 - Estimated enrollment, N = 56
 - Dates study start, primary completion: March 2015, June 2017).
 - Primary Outcome: Number of Tumor Infiltrating Lymphocytes (TILs) per high powered field (hpf) in resected pancreatic tissue and incidence of DLTs.
- Phase I/II Trial of MK-3475 and Hypofractionated Stereotactic Radiation Therapy in Patients with Non-Small Cell Lung Cancer (NSCLC) (NCT02444741)
 - Tumor: metastatic NSCLC
 - Treatment – phase 1: Pembrolizumab (starting at 100 mg) on Day 1 of each 3-week cycle + SBRT to lung (50 Gy, 4 fractions)
 - Treatment – phase 2: Pembrolizumab (at MTD determined in phase 1) + SBRT, or pembrolizumab + wide-field radiation therapy (WFRT).
 - Location/schedule of RT: SBRT to lung at 50 Gy over 4 fractions, or WFRT to lung at 45 Gy in 15 daily fractions
 - Estimated enrollment, N = 104
 - Dates study start, primary completion: Sept 2015, Sept 2020
 - Primary Outcome: MTD (phase 1), PFS/response (phase 2)

Reported results from the above studies will be followed to inform potential modifications, if appropriate, in the current trial.

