2.1.2 Secondary Objectives

- Determine the response rate by RECIST 1.1 and informed by irRECIST, of non-irradiated metastatic sites when pembrolizumab is combined with radiotherapy.
- Evaluate treatment-related toxicity.
- Evaluate PFS, OS, TTP, and DCR
- Explore the association between RR and other endpoints (e.g., OS, PFS)

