5.2.2.1 Dose specifications and technical factors

The trial administers a total dose of 20, 25, or 30 Gy over 5 fractions per metastatic lesion. The treating radiation oncologist may select the prescription dose to meet the tumor coverage requirements and the organ at risk constraints (OAR) as specified below. It is recommended that the highest dose possible be administered, so long as all mandatory organs at risk (OAR) criteria are met. General recommendations for dose based on lesion site are described below.

Total dose (Gy)	Fractions	Dose per fraction	Example sites
20-30	5	4-6	Liver, lung, bone (non-spine)
20-25	5	4-5	Abdomen/pelvis
20	5	4	Spine

Dose should be prescribed such that $\geq 95\%$ of the PTV receives the prescription dose. All mandatory OAR criteria must be met at a given radiotherapy dose level, or else the dose must be lowered to the next lowest dose level.

The energy of the treatment beam will be at least 6 MV and no greater than 18 MV. The use of intensity-modulated radiation therapy (IMRT) is allowed, however, proton beam radiation therapy and intraoperative radiotherapy (IORT) are NOT allowed. Radiation dose prescriptions will be calculated using heterogeneity corrections to take into account tissue inhomogeneities in treatment planning.

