9.7 Descriptive Factors

- RT to bone on this study: ever vs. never
- Number of metastases: 3 vs. 4-6 vs. 7-10 vs. 11 or more
- Number of anatomic regions involved (1-3: thoracic, abdominal/pelvic, or bone)
- Type of anatomic region involved (thoracic [yes/no], abdominal/pelvic [yes/no], bone [yes/no])

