12.2.2 Definition and Analysis of Secondary Endpoints

- Response rate (RR) by RECIST 1.1.
- Adverse events: The maximum grade for each type of adverse event will be summarized using CTCAE version 4.0. The frequency and percentage of grade 2+ adverse events will be assessed. We will also explore the treatment related adverse events as well (toxicities).
- Progression-free survival (PFS) is defined as the time from registration to the first of either disease progression or death from any cause, where disease progression will be determined based on RECIST 1.1 criteria. PFS will be estimated using the Kaplan-Meier method, where patients that are alive and progression-free will be censored on their last tumor evaluation date.
- Overall Survival (OS) is defined as the time from registration to death from any cause. OS will be estimated using the Kaplan-Meier method.
- Time-to-Progression (TTP) is defined as the time from registration to disease progression, where patients that are progression-free will be censored on their last tumor evaluation date. TTP will be estimated using the cumulative incidence method, where deaths will be treated as competing risks.
- Disease Control Rate (DCR) is defined as the frequency (%) of patients who have a best response of PR, CR, or Stable disease.
- The association between RR (using RECIST 1.1 (informed by irRECIST)) with other clinical endpoints (e.g., OS, PFS, etc.) will be performed. For time-to-event endpoints, we will use Cox proportional hazards models and Kaplan-Meier methodology. This analysis of RR as a predictor of OS, PFS, etc. will be based on a landmark analysis at various time points of interest post-baseline that correspond to expected tumor assessment time points. This will eliminate the possible response bias of patients living longer or doing better because they lived long enough to respond to treatment. For any associations of RR with categorical data, we will use Chi-square or Fisher's exact tests along with logistic regression models. Descriptive statistics and graphical techniques will be used to summarize this data. Given the small sample size, all these analyses will be considered hypothesis generating and exploratory.

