12.4 Assessment of Safety

Any subject who receives at least one dose of treatment on this protocol will be evaluable for toxicity. The National Cancer Institute (NCI) Common Terminology Criteria for Adverse Events (CTCAE) v4 will be used. The Study Calendar shows the schedule of toxicity assessments.

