12.7 Interim Analysis/Criteria for Stopping Study

Interim Analysis (based on primary endpoint): Enroll 14 eligible patients. If at least 2 confirmed responses are observed in the first 14 eligible patients, we will continue the trial to the second stage and continue the study to a full accrual of 29 eligible patients. Otherwise, the study will be permanently closed due to lack of efficacy. Accrual will continue during the interim analysis phase unless we observe a much higher than expected accrual rate or toxicity rate.

Final Analysis (based on primary endpoint): If the trial is a success during the interim analysis, we will enroll another 15 eligible patients to the second and final stage (29 eligible total). If at least 5 confirmed responses are observed in the first 29 eligible patients (17%), the treatment will be considered worthy of further investigation. Otherwise, the study will be permanently closed due to lack of efficacy.

Adverse Event Stopping Rule: The stopping rule specified below is based on the knowledge available at study development. We note that the Adverse Event Stopping Rule may be adjusted in the event of either (1) the study re-opening to accrual after any temporary suspension or (2) at any time during the conduct of the trial and in consideration of newly acquired information regarding the adverse event profile of the treatment(s) under investigation. The study team may also choose to suspend accrual because of unexpected adverse event profiles that have not crossed the specified rule below.

Accrual will be temporarily suspended to this study if at any time we observe events considered at least possibly related to study treatment (i.e., an adverse event with attribute specified as "possible", "probable", or "definite") that satisfy any of the following criteria:

- If at any time, 4 of the initial 10 treated patients or 40% or more of all patients (i.e. when accrual is greater than 10 patients) have experienced a Grade 4 non-hematologic adverse event.
- If at any time, 2 of the initial 10 treated patients or 20% or more of all patients (i.e., when accrual is greater than 10 patients) have experienced a Grade 5 adverse event (non -progressive disease).

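### Lung and liver RT with pembrolizumab is called a safety focus, but no toxicity analysis by irradiated organ is planned, so the planned rates are diluted by unexposed patients

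*Combined protocol and SAP*

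**What the plan says.** Section 1.4.2 reviews pneumonitis and hepatic events with pembrolizumab because RT may be given to lung or liver metastases, and says such RT could in theory worsen organ-specific toxicity. It then says "The safety and tolerability of lung/liver RT in combination of pembrolizumab has not been extensively examined" and, subject to safeguards in eligibility and design, that this "is a focus of the current trial".

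The irradiated site differs between patients. The dose table in 5.2.2.1 gives liver, lung, non-spine bone, abdomen/pelvis and spine as examples, and each patient is to have two sites treated (5.2.2).

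The later sections are general:

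- Objective (2.1.2): "Evaluate treatment-related toxicity". No organ or RT site is named.
- Safety population (12.4): "Any subject who receives at least one dose of treatment on this protocol will be evaluable for toxicity". The first dose is pembrolizumab on Day -21 (5.2), three weeks before RT begins.
- Analysis (12.2.2): "The maximum grade for each type of adverse event will be summarized using CTCAE version 4.0", plus the frequency and percentage of grade 2+ events. There is no split by irradiated site.
- Descriptive factors (9.7): the only irradiated-site item is "RT to bone on this study: ever vs. never". The thoracic, abdominal/pelvic and bone items describe where disease lies, not where RT was given, and liver is not separate.
- DSMB review (13.2): an adverse event summary report, with no mention of irradiated site.

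**The concern.** The background poses a question about patients whose lung or liver is irradiated while they receive pembrolizumab. The planned analysis answers a different one: how often each type of event occurs among all treated patients. A patient irradiated only at, say, two pelvic sites adds to the denominator but was never at risk from the lung combination. The same is true of a patient who stops after the Day -21 dose.

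Two misreadings could follow. If cases occur, the percentage understates the risk in exposed patients. If none occur, the upper bound looks tighter than the exposed patients can support. The second matters more in a small trial, because an absence of cases could be reported as evidence that the combination is safe at these organs.

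**Working it through.** **Plan's own figures.** Section 12.3 sets enrolment at 29 + 5 = 34, so 34 is the largest possible safety denominator. The documents give no precision for any toxicity rate and no expected number of patients with lung or liver RT, so there is no planned safety figure to reproduce.

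**Inputs.**
- Pooled denominator: n = 34 (12.3, 12.4).
- Exposed patients: not in the documents. Main assumption: 10 of 34. Range: 20-60% of 34, or about 7 to 20.
- Illustrative case count: x = 3 pneumonitis cases, all in lung-irradiated patients (assumed), or x = 0.
- Background rate: 7.8% radiation pneumonitis, from the retrospective series of combined-modality lung cancer therapy cited in 1.4.2. It is used only to see whether zero cases is a realistic outcome.

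**Formulas.**
- Exact 95% interval for x of n: lower limit is the 0.025 quantile of Beta(x, n - x + 1); upper limit is the 0.975 quantile of Beta(x + 1, n - x).
- One-sided 95% upper bound with zero events: 1 - 0.05^(1/n).
- Probability of at least one case at 7.8%: 1 - (1 - 0.078)^n.

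**Main example.**
- Three cases pooled: 3/34 = 8.8% (1.9-23.7%).
- Three cases among 10 exposed: 3/10 = 30% (6.7-65.2%).
- Zero cases pooled: 1 - 0.05^(1/34) = 8.4%.
- Zero cases among 10 exposed: 1 - 0.05^(1/10) = 25.9%.

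**Over the assumed range of exposed patients.**

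| Denominator | 3 cases: rate (exact 95% CI) | 0 cases: upper 95% bound |
|---|---|---|
| 7 exposed | 42.9% (9.9-81.6%) | 34.8% |
| 10 exposed | 30.0% (6.7-65.2%) | 25.9% |
| 14 exposed | 21.4% (4.7-50.8%) | 19.3% |
| 17 exposed | 17.6% (3.8-43.4%) | 16.2% |
| 20 exposed | 15.0% (3.2-37.9%) | 13.9% |
| 34 pooled | 8.8% (1.9-23.7%) | 8.4% |

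When all cases arise in exposed patients, the pooled rate is the exposed rate multiplied by (number exposed)/34. With 10 exposed, 30% x 10/34 = 8.8%. Cases in unexposed patients would narrow the gap.

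**Is zero cases realistic?** At 7.8%, the chance of at least one case is 43% with 7 exposed, 56% with 10 and 80% with 20. The chance of none is therefore 57%, 44% and 20%. A null result is quite possible even at that background rate, so the denominator behind its upper bound matters.

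**The case against.** The strongest reply is that the plan promises no lung- or liver-specific rate. The objective is general toxicity, and 12.2.2 and 12.4 match it. The word focus appears once, in the background, in a sentence tied to safeguards that do exist: chest- and heart-RT exclusions and a pneumonitis exclusion (3.2), and mandatory lung and liver dose constraints (5.2.2.5). This is fair as to formal commitments. But the safeguards lower risk; they do not estimate it, and a reader of 1.4.2 would expect the results to address the combination it singles out.

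The second reply is that the subgroups are too small to characterise safety. At 10 patients the interval runs from 7% to 65%. That is true, and it is why the tables should be descriptive. It does not favour pooling, which gives a narrower interval for a different quantity.

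The third is that lesion site is an imperfect measure of exposure. A rib or thoracic-spine field can deliver lung dose, and 1.4.2 itself links pneumonitis to V20 and mean lung dose. This stands, and the exposure definition in the fix allows for it.

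A reader might also infer three stronger things that the documents do not support:

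- *The irradiated site is not recorded.* Section 9.7 lists descriptive factors, not everything captured. Nothing says the site is left out of the RT records or the EDC system.
- *The trial cannot report the rate.* If the site is held, the rate can be produced at reporting. What is missing is a planned analysis.
- *The DSMB could miss a lung or liver signal because the stopping rule in 12.7 pools all patients.* That rule is not the only route. Events are summarised by type, so pneumonitis and hepatitis appear as counts. Serious Grade 4-5 events are reported within 24 hours (11.2.2.1), and the sponsor-investigator receives each SAE summary (11.4). The DSMB reviews at least every six months (13.2), and 12.7 lets the team suspend accrual without the rule being crossed.

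**Conclusion.** The point holds as a gap between a stated safety focus and the planned analysis. As written, the plan yields only whole-cohort percentages for pulmonary and hepatic events, and these are diluted for the question raised in 1.4.2. With 10 of 34 exposed, three cases read as 8.8% rather than 30%, and zero cases give an upper bound of 8.4% rather than 25.9%. Over 7 to 20 exposed patients, the correct zero-event bound runs from 34.8% down to 13.9%.

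The size rests on the assumed exposed share and on all cases falling in exposed patients. The direction holds whenever the event is more frequent in exposed than in unexposed patients. For zero events, the pooled bound is too tight whatever the share, provided some treated patients are unexposed.

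The primary endpoint and the decision rules are not affected. This is an inexpensive improvement that should be made, because it changes what the trial can say about the safety question it names.

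**What to change.** 1. In 9.7, add RT to lung/thorax (ever/never, counting any field that delivers lung dose), RT to liver (ever/never) and delivered dose level (20, 25 or 30 Gy, the levels in 5.2.2.1).
2. In 12.2.2, add two tables beside the whole-cohort one: pulmonary adverse events among patients with lung/thorax RT, and hepatic adverse events among patients with liver RT. Give each rate its own denominator and an exact 95% CI, and label the tables descriptive.
3. In 13.2, include the same two tables in the DSMB report.

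The stopping thresholds in 12.7 are unchanged. The cost is two extra tables built from RT records that treatment generates anyway, with no new procedures for patients. The drawback is wide intervals, which reflect what a trial of this size can show. Specifying the tables now avoids a split chosen after toxicity has been seen.
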